## 6.1 SCHEMA

This clinical study will investigate the utility of [F]FES in patients with estrogen receptor (ER) positive, primary, recurrent or metastatic, breast carcinoma. [F]FES PET has been validated as a measure of estrogen receptor expression. This trial is also designed to test the safety of [F]FES. In addition, this study will obtain data on the value of [F]FES to predict and evaluate response to endocrine-targeted therapies as a measure of ER expression in this patient population. If promising, these data will be used to design a phase II multi-center clinical trial.

We anticipate that the imaging measure of receptor density will predict the likelihood that a patient will respond to hormone targeted therapy, evaluate subsequent changes in this measure as the patient undergoes therapy and that eventually [F]FES imaging will help us design therapeutic trials for better treatment outcomes. We also expect that repeat [F]FES PET imaging shortly after the start of endocrine-targeted therapy will reflect the pharmacodynamics of endocrine targeted therapy.

This protocol is outlined in the following schematic. Briefly, patients with primary, recurrent or metastatic breast cancer from an ER+ primary tumor who will be undergoing endocrine-targeted therapy will be imaged with [F-18]-16 $\alpha$ -fluoroestradiol. All patients will undergo a pre-therapy FES PET or FES PET/CT scan (hereafter FES PET will be used to denote both FES PET and FES PET/CT unless specifically noted). In some patients receiving non-interfering medications such as aromatase inhibitors, scans may be performed with patients already on a treatment who are to start an alternative or additional endocrine targeted treatment. Patients will undergo a repeat FES PET and FDG PET on study after starting the endocrine-targeted therapy. The exact timing of the repeat scans may vary depending on the treatment regimen. In the repeat studies, we will be testing the ability of FES PET and FDG PET to measure the pharmacologic effect of endocrine-targeted therapy and early measures that may help predict response to such targeted agents. In patients on selective estrogen receptor degrader (SERD) therapies, where repeat FES PET is used primarily to evaluate residual ER availability rather than tumor response, repeat FDG PET may be omitted, as determined by requirements of the co-enrolling companion therapeutic protocol. A subset of patients may undergo a third FES PET at a later time point determined by the treatment regimen.

FDG PET and CT will be used as staging tests for this study and FDG will also serve as a comparator for tumor localization with the FES imaging. Patients will have a clinical FDG PET scan prior to the start of treatment as part of their standard care; their treating physician will order this. In rare cases where an FDG PET has recently been performed at an outside medical facility but the scan has (1) inadequate image quality or (2) insufficient quantitative information, or for patients who would not be ordered as a standard part of the patient's care, a baseline FDG scan will be done as part of this protocol. A second FDG PET scan will be done as a study procedure concurrent with the FES PET timing stipulated by treatment regimen (this may vary from 1 to 12 weeks post treatment start depending on regimen). In the subset of patients undergoing a third

FES PET scan there may also be a research FDG PET done at the same time point if determined by the treatment regimen.

[figure not shown]
After the FES and FDG baseline imaging (see schematic below), the patients will start or change therapy, typically within 30 days, and be followed clinically for up to 20 years. Lesion location will be identified using clinical FDG scans with reference to clinical CT for metastatic disease or ultrasound, mammography, and/or breast MRI for primary tumors in patients presenting with metastatic or recurrent disease that still have a primary breast lesion. FES and FDG images will be spatially co-registered and tumor regions will be drawn on the FDG images and transferred to the FES images for quantitative analysis of FES uptake in both ER positive and ER negative tumors. For FDG studies, SUVs will be generated.

The FES uptake from images will be analyzed qualitatively by visual assessment and quantitatively using a standard uptake value (SUV). Serial measurements of hormone levels in peripheral blood may be used with some treatment regimens to allow determination of efficacy of endocrine therapy. ER, PR and HER2 assays will allow determination of hormone receptor status and whether HER2 over-expression indicates estrogen-independent growth in some treatment studies, however, there may not be pathologic correlates in all studies.

**We emphasize that this is an observational study in that [F]FES PET will not be used to direct therapy.** Treatment regimens are chosen by the referring oncologist prior to the [F]FES PET study on the basis of clinical criteria or participation in experimental treatment protocols. While patients and referring physicians will not be blinded to [F]FES PET results, treatment choices will be made prior to the entry of the patient into the study and will not be altered because of the FES PET results.

Patients with metastatic or recurrent disease may consent to optional research biopsies performed prior to start of the selected endocrine-targeted therapy, and after 1-12 weeks on therapy. Obtained tissues will be analyzed for expression of prognostic markers and/or for intra-tumor steroid hormone concentrations to evaluate correlations between results of imaging and histo-pathological studies and to enhance understanding of mechanisms of response and resistance in the context of tumor microenvironment.

**Figure 6.1** Outline (Schema) of the [F]FES Study Protocol. a) FDG PET is not required for primary breast cancer patients unless required for localization or requested by treating physician. b) Where available and medically appropriate, a clinical or research biopsy that involved sampling of a relevant lesion within 6 months prior to the enrollment may be utilized in place of the baseline optional biopsy. c) Repeat FDG PET may be omitted in patients on SERD therapies.

## 6.2 OBJECTIVES

### 6.2.1 Primary Objective

Measure the effect of endocrine targeted therapy on ER expression and estradiol binding to the receptor using serial FES PET and FDG PET.

### 6.2.2 Secondary Objectives

Document the safety profile of FES PET in patients with breast cancer.

Examine associations between FES PET results and serial measurements of hormone or other levels in peripheral blood, as related to efficacy of endocrine-targeted therapy. Correlate FES PET uptake measures with histopathological assays and tumor microenvironment studies on biopsy specimens, if relevant to specific treatment regimen.

## 6.3 BACKGROUND

### 6.3.1 Study Disease

**6.3.1.a Invasive breast carcinoma:** In 2007, breast cancer will be diagnosed in over 180,000 women and account for over 40,000 deaths in the United States (Jemal, 2007b). The incidence of hormone receptor positive disease appears to be increasing (Li, 2003). Advances in diagnosis and therapy have resulted in increased survival for early breast cancer (Jemal, 2007a; Piccart-Gebhart, 2005; Romond, 2005; Winer, 2005; Jemal, 2006). This increase in breast cancer survival may result in more patients diagnosed with advanced or metastatic breast cancer. Improved and targeted treatment of advanced breast cancer has also resulted in improved outcomes (Chia, 2003). However, better tailoring of therapy to patients is likely to result in higher quality of life (Greenberg, 1996).

**6.3.1.b Invasive breast carcinoma and hormone receptors:** Nearly two-thirds of breast cancer patients have hormone receptor bearing (HR+) tumors (Carlson, 2002). Treatment options for HR+ patients have expanded to more potent and less toxic therapies, inviting clinicians to offer endocrine therapy to more patients (Carlson, 2002; Lonning, 2001). Nonetheless, chemotherapy is frequently offered to patients without proof of superior outcomes. Measurement of tumor hormone receptor expression, both estrogen receptor (ER) and progesterone receptor (PgR) at the time of primary diagnosis is now the standard of clinical care (Carlson, 2004). Knowledge of hormone receptor expression is essential for selection of

appropriate therapy but biopsies and serum assays may not provide sufficiently complete information (Anonymous, 1998; Osborne, 1998).

**6.3.1.c Treatment of breast carcinoma:** Treatment selection for breast cancer poses several challenges. Heterogeneity is a challenge in management of breast cancer, especially for locally advanced or metastatic disease. In cases where tissue sampling is feasible, the expression of ER may be heterogeneous, and ER expression at one site does not guarantee expression at all sites. This issue presents significant practical challenges for assessing ER expression in breast cancer. The potential for misidentification of patients appropriate for endocrine therapy is significant. While ER expression predicts measurable tumor regression (objective response) in 30% to 77% of patients with a new diagnosis of breast cancer, response rates are more typically 7% to 21% in patients with recurrent disease and prior breast cancer treatment (Lonning, 2001). A predictive assay of hormone sensitivity capable of assessing ER expression at all sites of disease would be highly valuable for selection of which patients are more likely to benefit from endocrine therapy.

**6.3.1.d Recent advances in endocrine therapy:** A significant advance in the management of ER+ metastatic breast cancer is the introduction of aromatase inhibitors (AI) (Winer, 2005; Mouridsen, 2001; Nabholz, 2000). These agents are more effective and result in a longer time to progression than previous therapies, and have therefore displaced tamoxifen as first-line treatment for metastases and adjuvant therapy (Winer, 2005; Mouridsen, 2001; Nabholz, 2000, Carlson 2005). However, several endocrine therapies are active agents for the treatment of hormone responsive disease: fulvestrant, a selective estrogen receptor demodulator agent or SERD; tamoxifen, a selective ER blocking drug, or SERM; as well as megestrol, testosterone, and diethylstilbesterol (DES) (Lonning, 2001; Carlson, 2005; Osborne, 2002; Buckner, 1989). Increasing use of AIs in the adjuvant setting will lead to increased use of alternative endocrine treatment strategies in the metastatic setting.

**6.3.1.e Endocrine therapy for breast carcinoma:** The optimal management of patients who experience progression of disease while on adjuvant aromatase inhibitor treatment, and of premenopausal patients, remains under investigation. There is evidence to support the usefulness of irreversible steroidal AIs (exemestane) for treating patients who progress on nonsteroidal AIs (Lonning, 2000). Clinical experience suggests a primary role for this strategy in patients who have a significant disease-free interval on a hormonal adjuvant therapy. Currently active investigational protocols will determine the optimal management of premenopausal women with hormonal therapy. However, tamoxifen remains standard management and tamoxifen therapy in pre-menopausal patients may be complicated by high estradiol levels due to tamoxifen

stimulation of the ovary (Jordan, 1991; Sunderland, 1991). Ovarian suppression alone or with tamoxifen or an AI is also an effective strategy (Carlson, 2004; Davidson, 2000; Klijn, 2000; Klijn, 2001; Milla Santos, 2002), but the optimal sequence of endocrine treatment in premenopausal patients is not yet clear (Prowell, 2004). Our study will test the value of FES PET for predicting the effectiveness of endocrine therapy, with the eventual goal of selecting patients with primary or metastatic disease most likely to benefit from this expanding choice of agents for endocrine therapy. In addition, our hypothesis is that FES PET will be useful as a predictive assay for those patients who have failed one endocrine therapy agent and are being considered for an alternative endocrine treatment.

**6.3.1.f Imaging of ER with [F]FES:** PET ER imaging using [F]-fluoroestradiol (FES) poses an attractive possibility to meet this clinical need. Previous work evaluating the ER binding, radiation dosimetry, blood clearance and protein interactions of FES in women with hormone receptor positive breast cancer has shown that uptake correlates with in vitro assay of expression in breast cancer tissue samples (Mankoff, 2001; Mintun, 1988). Furthermore FES positron emission tomography (with either PET or PET/CT) measures the heterogeneity of ER expression and function in metastatic disease (Mankoff, 2002; Dehdashti, 1995). Prior studies have shown that the level of FES uptake predicts the response of advanced breast cancer to hormonal therapy; these therapies were predominantly tamoxifen (Mortimer, 2001). We also showed that the level of FES uptake as an in vivo indicator of ER function predicted response to endocrine therapy (Linden, 2006). We measured FES uptake in patients with recurrent or metastatic breast cancer treated largely with aromatase inhibitors. In this study we will test FES predictive capability in patients undergoing endocrine therapy of breast cancer, and also to test the effect of ER-directed breast cancer treatments on ER expression and/or ER blockade.

### **6.3.2 Investigational Agent**

**6.3.2.a 16 $\alpha$ -[F]-fluoro-17 $\beta$ -estradiol (FES)** is a radiolabeled imaging agent that has been used for investigating tumor estrogen receptor activity with positron emission tomography (PET). It was developed in a collaboration of the Welch and Katzenellenbogen laboratories (Kiesewetter, 1984) as a positron-emitting radiopharmaceutical for imaging ER expression. Studies have shown that the strength ( $K_D$ ) of FES binding to the ER is nearly identical to estradiol (Kiesewetter, 1984). FES binding to sex steroid transport protein (SBP or SHBG) is also nearly identical to estradiol (Kiesewetter, 1984; Tewson, 1999). Fluorine-18 labeled FES can be synthesized with high specific activity so the quantity of estrogenic material injected with the radiopharmaceutical is <5  $\mu$ g (Kiesewetter,

1984; Lim, 1996). The typical peak molar concentrations of [F]FES from a [F]FES injection is 1 pmol/mL, a value comparable to circulating estrogen levels. This value decreases by 60 minutes post-injection to 0.05 pmol/mL. [F]FES can generate high quality PET images of regional estradiol binding using a 6 mCi injection, with acceptable radiation dose to the patient (Mankoff, 2001). In breast cancer, the uptake of FES measured by PET has been shown to correlate with ER expression in biopsy material assayed by in vitro radioligand binding (Mintun, 1988) or by immunohistochemistry (Peterson, 2008). As has been found for in vitro assays of ER expression, the level of FES uptake in breast cancer is predictive of response to endocrine therapy in advanced tumors treated with primary tamoxifen therapy (Mortimer, 2001) and metastatic cancer treated by salvage hormonal therapy, mostly in the form of aromatase inhibitors (Linden, 2006). This protocol will evaluate FES as an in vivo predictive assay for endocrine therapy of newly diagnosed metastatic breast cancer.

### **6.3.3 Rationale**

- 6.3.3.a** The primary hypothesis to be tested is that pre-therapy and post-therapy [F]FES uptake will measure the effect of endocrine-targeted therapy on ER expression and/or estradiol binding to the ER.
- 6.3.3.b** This single-site study will determine the ability of [F]FES to quantify changes in ER expression and estradiol binding in vivo in patients with breast cancer for whom endocrine-targeted therapy has been chosen based on clinical presentation or as part of therapeutic clinical trial. The results of this trial will help evaluate the effect of ER-directed therapies on ER expression and estrogen binding to ER, and secondarily whether the FES PET measures of estrogen receptor function, and changes with treatment, predict response to endocrine targeted therapy in patients with known ER+ primary or metastatic breast cancer as measured by immunohistochemistry (IHC) of biopsy material. The primary goal is to gain insight into the efficacy of ER-targeted therapies, especially novel therapies, on ER expression and estrogen binding to ER. For example, serial FES PET imaging could be used to test the efficacy of an ER antagonist in blocking estradiol binding, or the ability of an agent directed at altering ER expression to change ER expression levels in tumors. Such in vivo measures of the pharmacodynamics of ER-directed therapy have traditionally required serial biopsy and have been quite challenging. FES PET presents a non-invasive alternative to measure the effects of ER-directed therapy.
- 6.3.3.c** We have examined the role of FES in 47 heavily pretreated patients (Linden, 2006). Initial FES uptake was measured and correlated with subsequent tumor response to 6 months of hormonal treatment. In this

study, 11/47 (23%) patients had an objective response. Quantitative FES uptake and response were significantly associated; 0/15 patients with initial FES SUV < 1.5 responded to hormonal therapy, compared to 11/32 (34%) with FES SUV ≥ 1.5 ( $p < .01$ ). In the subset of patients whose tumors did not over-express HER2/neu, 11/24 (46%) of patients with SUV ≥ 1.5 responded. These pilot results support the further evaluation of the predictive capability of FES PET.

- 6.3.3.d** FES uptake predicted a greater likelihood of response to endocrine therapy. Patients with low or absent FES uptake were unlikely to manifest a response to treatment, yet FES did not help to distinguish which patients would experience a clinical benefit, defined as stable disease. Several factors may have contributed to this finding. Stable disease over 6 months included patients with disease that may have progressed slowly, independent of treatment, as well as patients with rapidly progressive disease in whom therapy slowed but did not abrogate tumor growth. The study was not designed to distinguish between these two outcomes. In addition, we identified PgR (progesterone receptor) expression as contributing to likelihood of response, and noted that elevated estradiol levels and HER2 expression were associated with non-response. In this new study we propose to document tumor characteristics including quantitative ER mRNA levels measured by PCR and semi-quantitative levels of ER, PgR, AR and HER2 by IHC. Gathering these indices as part of the proposed study may help to enhance the predictive value of PET FES, allow understanding of mechanism of resistance to endocrine therapy, and potentially determine which patients are likely to appreciate clinical benefit as a result of endocrine therapy, even in the absence of an objective response.
- 6.3.3.e** In prior observational imaging trials (unpublished data) we have measured regional estrogen-ER binding using FES PET before and after treatment with estrogen depleting therapies, Aromatase inhibitors (AI), and estrogen blocking therapies, Tamoxifen (TAM), or fulvestrant (FUL) in 30 metastatic breast cancer patients. As expected, tumor FES uptake declined markedly on ER blockers TAM and FUL (average 54% decline), but less than 15% on average on estrogen-depleting AIs ( $p < 0.001$ ). All 5/5 patients taking TAM showed complete tumor blockade (FES SUV ≤ 1.5 after treatment), compared to 4/11 of FUL patients ( $p = 0.009$ ). We concluded that molecular imaging can assess the *in vivo* pharmacodynamics of targeted agents, and may give insight into the activity of established therapeutic agents.

## **6.4 PATIENT SELECTION**

### **6.4.1 Inclusion Criteria:**

- 6.4.1.a** Adult, non-pregnant patients with biopsy-proven or clinically obvious primary, recurrent or metastatic breast cancer
- 6.4.1.b** Breast cancer from ER+ primary that is seen on other imaging tests. Tumor ER expression must have been confirmed by immunohistochemistry of primary tumor or recurrent disease.
- 6.4.1.c** At least one site of disease 1.5 cm or greater is needed to meet the spatial resolution limits of PET imaging.
- 6.4.1.d** Patients must have been off tamoxifen or other estrogen receptor blocking agents for at least 6 weeks and off chemotherapy for 3 weeks for the initial baseline FES.
- 6.4.1.e** Patients must be selected for an endocrine targeted therapy regimen for treatment of their breast cancer by the referring oncologist. Selected treatments may be part of experimental treatment protocols for which the patient would be separately consented.
- 6.4.1.f** Patients must be willing to undergo serial imaging procedures.
- 6.4.1.g** Patients must agree to allow access to clinical records regarding response to treatment and long term follow up.

### **6.4.2 Exclusion Criteria:**

- 6.4.2.a** An inability to lie still for the tests
- 6.4.2.b** Individuals weighing more than 300 lb. (this is the weight limit of the scanner table)
- 6.4.2.c** Pregnant or lactating. Women of childbearing potential with either a positive or no pregnancy test at baseline are excluded.
- 6.4.2.d** Any other life-threatening illness (e.g. serious, uncontrolled concurrent infection or clinically significant cardiac disease – congestive heart failure, symptomatic coronary artery disease, cardiac arrhythmia not well controlled with medication).
- 6.4.2.e** Use of tamoxifen, faslodex, DES or any other ER blocking agent < 6 weeks or chemotherapy < 3 weeks prior to imaging scan.

**6.4.2.f** Unwillingness or inability to give informed consent.

**6.4.2.g** Uncontrolled diabetes mellitus (fasting glucose > 200 mg/dL)

**6.4.2.h** Adult patients who require monitored anesthesia for PET scanning.

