**6.5 REGISTRATION PROCEDURES**

Not applicable; this is a single-institution trial

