**6.6.1 [F]FES Administration:**

FES will be administered in the PET imaging suite at the University of Washington Medical Center or at the Seattle Cancer Care Alliance (SCCA). The [F]FES for injection will be prepared as described in section 6.6.2, Study Procedures and Schedule of Events. Upon arrival, the patient will have an opportunity to have questions answered regarding the procedure. The patient will have an intravenous line placed prior to [F]FES administration. A dose of nominally 220 MBq (6 mCi with a range of 110 to 220 MBq = 3 to 6 mCi) of [F]FES will be administered intravenously by a physician. The injection will be infused over approximately 2 minutes and followed by a saline flush. The infusion and imaging procedure will be terminated in any patient who exhibits anaphylaxis, physical signs of significant hypotension, significant dyspnea or chest pain. We do not expect to observe any of these effects as no events have been reported in more than 300 scans performed with this compound at our institution to this date. The patient will then be allowed to rest comfortably in a prep room prior to being positioned in the PET scanner to commence the image acquisition at 60 +/- 10 minutes post FES injection.

Heart rate and blood pressure will be recorded pre- and post-FES dosing, and will continue to be monitored after injection until baseline is achieved.

Patients will be monitored for adverse events, potentially related to the administration of [F]FES, from the time of the initial injection to 10 hours post injection. Any adverse events will be recorded and reported according to FDA requirements (see section 6.8 Adverse Events).

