## 6.6.2 Study Procedures and Schedule of Events

**6.6.2.a Initial visits prior to [F]FES PET:** Patients who are identified as potential candidates for the [F]FES PET study will be approached to explain the nature of the study and to obtain their written informed consent to be enrolled in the protocol. Heart rate and blood pressure will be recorded at the time of clinic visit where study is considered or at the time of consent. The patient will have a clinical FDG PET/CT scan if a recent FDG scan has not already been obtained. The FDG PET/CT scan should be obtained close to the time of FES PET/CT, typically within 14 days of the [F]FES PET/CT scan. An additional FDG PET/CT scan may be done as a research scan if the patient has undergone a recent PET scan at an outside institution or if they are unable to obtain a clinical PET scan as part of their clinical care. The research FDG PET/CT scan in this instance will be identical in procedure to a clinical FDG scan. The following additional patient data will be obtained: histological diagnosis, age at radiologic diagnosis, weight, gender, ECOG score and other treatment modalities used. Correlative radiology including CT, MRI, or bone scan, and laboratory tests measuring renal, blood and liver function will also be collected, typically for values within 30 days of the FES PET/CT scan. For patients referred from outside the UW health system, patient records, and biopsy material and imaging as necessary, will be reviewed to determine eligibility for the study.

**6.6.2.b Day of [F]FES PET/CT Scan:** After the FES injection and rest period (section 6.6.1), the patient will be positioned supine in the PET/CT scanner. A low dose CT scan (60 mA) will provide attenuation correction data using non-contrast CT. The PET image acquisition sequence will be the same as that used for clinical FDG scans. This consists of a torso survey series of five-minute images acquired over 15 cm survey fields of view (FOVs) extending from the base of the skull to the mid thigh (5 to 7 FOVs in total). The images will be corrected for radioactive decay of the tracer and normalized to the injected dose and body weight. This results in regional standardized uptake values (SUVs) whole-body image sets.

Prior to injection, a whole blood sample may be taken for determination of albumin, estradiol and testosterone levels, heart rate and blood pressure

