## 6.11 STUDY CALENDAR

Baseline evaluations are to be conducted prior to administration of protocol therapy, typically within 30 days. Baseline FDG PET/CT scan will be obtained near the time of the [F]FES-PET/CT scan, typically within 14 days. Procedures are outlined below in Table 6.2.

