**Table 6.2. Study Calendar.**

	Pre-Study	Imaging 1	Rx 1	Imaging 2 	Rx 2	Imaging 3 	Follow up
Informed Consent	X						
Demographics	X						
Pregnancy Test 	X						
Vital Signs 		X		X		X	
Research lab tests 		X		X		X	
ER, PgR, HER2 	X						
FDG PET/CT 	X			X		X	
[  F]FES injection and PET 		X		X		X	
Collect serum hormone levels 		X		X		X	
Adverse Event Evaluation		X (0-24hr)		X (0-24hr)		X (0-24hr)	
Optional tumor tissue biopsy and blood draw 		X		X			

 If patient is pre-menopausal, and birth control use is not confirmed

 Vital signs include heart rate and blood pressure

 Additional blood tests to measure hormone levels (e.g. estradiol, estrone, testosterone, DHT, SHBG) or other hormone related measures might be performed in some patients depending on the treatment regimen.

 Pathology results from primary or metastatic biopsy will be reviewed and additional pathology tests may be performed on some patients depending on the treatment regimen.

 FES PET/CT and FDG PET/CT will be done at 1-12 weeks after the Imaging 1 time point depending on the treatment regimen.

 Repeat FDG PET may be omitted in patients on SERD therapies.

 FES PET/CT and FDG PET/CT may be done at 1-12 weeks after the Imaging 2 time point depending on the treatment regimen.

 Optional blood sample for estradiol, estrone, follicle-stimulating hormone, sex hormone binding globulin, testosterone and free testosterone serum levels.

 In patients consented to optional biopsies, obtain metastatic or recurrent tumor tissue from an FDG and/or FES avid site after completion of PET imaging but prior to start of the endocrine targeted therapy. Repeat the biopsy from the same site after 1-12 weeks on treatment. (Where available and medically appropriate, a clinical or research biopsy that involved sampling of a relevant lesion within 6 months prior to the enrollment may be utilized in place of the baseline optional biopsy.) A blood draw done during the same time point will accompany some biopsies.

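### The exclusion criterion requires a baseline pregnancy test in every woman of childbearing potential, but the study calendar drops the test when birth control is confirmed

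*Combined protocol and SAP*

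**What the plan says.** Two places in the combined protocol and SAP name the pregnancy test.

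- **Section 6.4.2.c (Exclusion Criteria):** "Women of childbearing potential with either a positive or no pregnancy test at baseline are excluded". The criterion treats a missing result in the same way as a positive one.
- **Section 6.11, Table 6.2 (Study Calendar), footnote 1:** the table marks a pregnancy test in the pre-study column, and the footnote attaches two joint conditions to it: "If patient is pre-menopausal, and birth control use is not confirmed". Section 6.11 introduces the table with "Procedures are outlined below in Table 6.2".

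Other sections bear on the point without settling it.

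- **Section 6.4.1.a** admits "Adult, non-pregnant patients with biopsy-proven or clinically obvious primary, recurrent or metastatic breast cancer". It does not say how non-pregnancy is to be established.
- **Section 6.6.2.a**, on the visits before the FES scan, says that "laboratory tests measuring renal, blood and liver function will also be collected". It does not mention a pregnancy test.
- **Sections 6.6.1 and 6.6.2.b**, on the day of injection, cover the intravenous line, vital signs, optional blood sampling and the scan, again without a pregnancy check.
- **Section 6.5 (Registration Procedures)** reads "Not applicable; this is a single-institution trial".

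The term childbearing potential is not defined anywhere in the available text.

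**The concern.** An eligibility criterion and the calendar that puts it into practice should give the same answer for every patient. Here they do not. The criterion makes a negative baseline test a condition of entry for all women of childbearing potential. The calendar tells staff that the test is needed only in some of them, which implies that the others may go without.

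Two things are at stake. The first is eligibility: a patient handled exactly as the calendar directs could be enrolled although the protocol excludes her, which is a protocol deviation. The second is radiation safety: she could receive the tracer and a CT without the check that the protocol made mandatory.

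The point concerns baseline only. Neither text asks for a repeat test before the second or third scan, so later scans are outside it.

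**Working it through.** No alpha, power or sample-size figure is involved, and the plan states no number to reproduce. The check compares the two rules for each type of patient.

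**Inputs**

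- Rule A (6.4.2.c): a woman of childbearing potential is excluded if her baseline test is positive or was not done.
- Rule B (Table 6.2, footnote 1): the test is called for if the patient is pre-menopausal *and* birth control use is not confirmed.

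**Comparison**

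| Patient | Rule B: test called for? | Rule A: result if only Rule B is followed | Consistent? |
|---|---|---|---|
| Of childbearing potential, pre-menopausal, birth control not confirmed | Yes | Eligible if the test is negative | Yes |
| Of childbearing potential, pre-menopausal, birth control confirmed | No | No test at baseline, so excluded | **No** |
| Not of childbearing potential, for example post-menopausal | No | Rule A does not apply | Yes |

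The conflict is confined to the second row.

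**Does another section close the gap?** No. Sections 6.4.1.a, 6.5, 6.6.1, 6.6.2.a and 6.6.2.b neither call for the test nor qualify either rule. Testing every woman of childbearing potential would satisfy both texts, but no procedure says to do so.

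**Can such a patient enrol?** Footnote 1 is the best evidence that she can, since its condition only makes sense if pre-menopausal women with and without confirmed birth control are expected. No criterion in 6.4.1 or 6.4.2 restricts menopausal status. The background in 6.3.1.e also discusses this group, noting that "the optimal sequence of endocrine treatment in premenopausal patients is not yet clear", although that passage is about treatment and not about enrolment.

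**Exposure per affected patient at baseline**

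- One FES injection. Section 6.6.1 sets "A dose of nominally 220 MBq" with a range of 110 to 220 MBq (3 to 6 mCi).
- One low-dose CT for attenuation correction (60 mA, section 6.6.2.b).
- Baseline FDG PET is not counted because it is usually part of standard care. Sections 6.1 and 6.10.1 allow it as a research scan in rare cases.

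**Number affected.** Table 6.4 plans 50 women and no men. The documents give no proportion who are pre-menopausal or who use contraception, so no estimate is made.

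**The case against.** The strongest reply is that the controlling text is already the safe one. Section 6.4.2.c names the situation in question and excludes the patient. Footnote 1 neither waives that exclusion nor forbids a wider test. An untested injection would need staff to follow a footnote and overlook an explicit criterion. On this view the matter is housekeeping.

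That argument limits the severity but does not remove the conflict. The calendar is where the protocol sets out its procedures, and a footnote saying when a test is needed will be read as saying when it is not.

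A second reply is that childbearing potential may be meant to leave out women with confirmed contraception, with footnote 1 showing how the site applies the term. This would reconcile the texts, but the protocol does not say it. It would also loosen a safety criterion through an unwritten definition. If that is the intention, an amendment is still needed to state it.

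Several narrower points stand:

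- The laboratory sentence in 6.6.2.a describes data to be collected and does not claim to list every pre-scan test. The absence of a pregnancy test there is not a separate defect.
- Section 6.5 says only that registration procedures do not apply. It does not show that eligibility goes unchecked, and 6.6.2.a does mention an eligibility review of records for patients referred from outside.
- Section 6.1 allows FES PET as well as FES PET/CT, so the CT component is not certain for every patient.
- The number affected may be zero.

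**Conclusion.** The inconsistency is real and should be fixed. For a pre-menopausal woman of childbearing potential with confirmed birth control, the calendar calls for no test and the exclusion criterion disqualifies her for having none.

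The consequence is a possible eligibility deviation and an avoidable radiation-safety gap at baseline: per affected patient, one FES injection of 110 to 220 MBq and, where PET/CT is used, one low-dose CT. How many patients this involves cannot be determined from the documents. The endpoints, the sample size and the power calculations in 6.14.1 are not affected.

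The conclusion rests on two assumptions. Childbearing potential is taken in its ordinary sense, so that using contraception does not remove a woman from it. And no removed page, such as the consent form, schedules the test more widely.

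**What to change.** Keep the stricter rule and bring the calendar into line with it. In Table 6.2, replace the condition in footnote 1 with *All women of childbearing potential*, so that the birth-control condition disappears. This one change resolves the conflict.

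Two further edits are optional but worth making in the same amendment:

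- Define childbearing potential once, in 6.4.2.c, stating whether contraception has any bearing on it.
- Add the pregnancy test to the pre-scan procedures in 6.6.2.a, with the negative result confirmed before the first FES injection.

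If the sponsor instead intends to exempt women with confirmed contraception, the exemption should be written into 6.4.2.c. That would weaken the current safeguard and is not the preferred route.

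The cost is one footnote and, if the optional edits are taken up, one definition and one line of procedure. A few more patients may have a routine test, which 6.4.2.c already requires. The sample size, imaging schedule and analysis do not change.
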